6.7. Treatment Exposure

Treatment exposure is estimated using each patient's first dose and last dosing date. If the first dosing date is missing, it will be imputed with the date of randomization. If the last dosing date is missing, it will be imputed with the date the patient discontinued treatment, discontinued the study, or completed the 36-week (Visit 9) or 52-week (Visit 11) treatment period, whichever is earlier.

Exposure will be calculated for each patient. It will then be summarized descriptively by treatment for the ITT Population.

6.8. Important Protocol Deviations

Important protocol deviations will be summarized descriptively by treatment and listed for all randomized patients. All important deviations related to study inclusion or exclusion criteria, conduct of the trial, patient management, or patient assessment will be described. The rationale for choosing certain important protocol deviations as exclusionary from the PP Population will be based on their potential effect on the primary efficacy measure. The following protocol conditions as well as other conditions identified at the site and agreed upon by the study team may result in exclusion from the PP Population along with the criteria listed in [Table GBGL.2](#):

- informed consent was never obtained
- patients who are randomized but the informed consent date is missing
- patients who have an HbA1c $<7.5\%$ or $>11.0\%$ at study entry (Visit 1)
- patients who have known type 1 diabetes
- patients who had any hematologic condition that may have interfered with HbA1c measurement (for example, hemolytic anemias, sickle-cell disease)
- excluded medication:
 - weight loss agents if the duration of use is 14 days (cumulative) during the treatment period
 - any new glucose-lowering medication initiated after randomization at Visit 3 and prior to Visit 11 (end of treatment period) for >14 days, except for study drug, rescue therapy, glucose-lowering medications initiated after study drug discontinuation, or short-term use of insulin (≤ 14 days) for management of medical emergencies
 - >14 consecutive days' use of systemic glucocorticoid during the treatment period

- patients who have a missing HbA1c at baseline (both Visit 1 and Visit 3) or at 36 weeks (Visit 9)
- patients who do not have an overall compliance with study drug of at least 75% up to 36 weeks

6.9. Efficacy Analyses

6.9.1. Primary Efficacy Analysis

6.9.1.1. Primary Outcome and Methodology

There will be 2 primary estimands to compare each investigational dulaglutide dose and dulaglutide 1.5 mg in terms of the primary measure of HbA1c change from baseline to Week 36 (Visit 9). See Section 6.1.

For each type of estimand, the 2 investigational doses will be tested versus dulaglutide 1.5 mg simultaneously, controlling the 2-sided alpha of 0.05. Each of the estimands will be tested separately with a full 2-sided alpha of 0.05.

For the efficacy estimand, an MMRM will be employed as the primary analysis of on-treatment without rescue data described in Section 6.1.

For the treatment-regimen estimand, an ANCOVA model will be applied as the primary analysis to the complete data using multiple imputation (Section 6.1.2.1). The model terms include pooled country and treatment as fixed effects, and baseline HbA1c as a covariate. The estimates and standard errors from the imputed datasets will be pooled (Little and Rubin 1987). The inference will be made through the pooled estimates.

6.9.1.2. Additional Analyses of the Primary Outcome

Different populations including the PP and Completers populations will be evaluated separately using the same model as described in Section 6.1. The goal for these analyses is to assess the robustness of the primary outcome.

6.9.2. Secondary Efficacy Analyses

6.9.2.1. Primary Analyses for Secondary Efficacy Endpoints

6.9.2.1.1. Efficacy Estimands

Each continuous variable (changes from baseline in body weight and in FSG) will employ the MMRM described in Section 6.9.1 by replacing baseline HbA1c with the corresponding baseline measurement as a covariate, and adding baseline HbA1c strata as a fixed effect.

The proportions of patients achieving HbA1c target <7.0% will be analyzed using the longitudinal logistic regression model described in Section 6.1. Pooled country, treatment, visit, and the treatment-by-visit interaction will be included as fixed effects with baseline HbA1c as a covariate.

6.9.2.1.2. Treatment-Regimen Estimands

An ANCOVA model will be fit to the complete data for each continuous variable (change from baseline in body weight and in FSG). In this model, pooled country, baseline HbA1c strata, and treatment will be fit as fixed effects, and corresponding baseline measure as a covariate. The missing data will be imputed (Section 6.1.2.1).

A logistic regression model will be fit to the complete data to analyze the proportions of patients reaching HbA1c target <7.0%. Pooled country and treatment will be included as fixed effects, and baseline HbA1c as a covariate. Missing data will be imputed as not achieving the target (Section 6.1.2.2).

The inference will be made through the pooled estimates using Rubin's rule (Little and Rubin 1987).

6.9.2.2. Supportive Analyses for Secondary Efficacy Endpoints

A logistic regression model will be fit with pooled country and treatment as fixed effects, and baseline HbA1c as a covariate to analyze the proportion of patients who achieved HbA1c targets. Prior to this analysis, the missing data at Week 36 (Visit 9) or the patients rescued and/or discontinued prior to Week 36 (Visit 9) will be imputed as not achieving HbA1c target.

The same logistic regression model will be applied to HbA1c targets using LOCF to impute missing data at Week 36 (Visit 9). The latter result will be generated along with the corresponding longitudinal analysis report (Section 6.9.2.1.1).

The analyses listed in the protocol using MMRM for the treatment-regimen estimand will not be carried out because they are replaced with the method described in Section 6.9.2.1.2.

6.9.3. Planned Exploratory Analyses

Some of the planned exploratory analyses are described in Section 6.1. The remaining exploratory analyses are described in this section.

The analyses of proportions of patients reaching each target: HbA1c target $\leq 6.5\%$, body weight loss $\geq 5\%$, and body weight loss $\geq 10\%$ will employ the logistic regression model described in Section 6.1. The model for body weight target will be changed by replacing baseline HbA1c with baseline body weight as a covariate along with baseline HbA1c strata as a fixed effect. HbA1c target of the below 2 composite endpoints using LOCF will only apply a logistic regression model with an additional covariate of baseline body weight.

- HbA1c <7.0%, no body weight gain, and no documented symptomatic or severe hypoglycemia
- HbA1c <7.0%, body weight loss $\geq 5\%$, and no documented symptomatic or severe hypoglycemia

Longitudinal continuous variables (up to 52 weeks) such as HbA1c, body weight, FSG, and calcitonin will be analyzed using the MMRM described in Section 6.1. If the normality assumption is violated, an appropriate data transformation may be applied prior to analysis.

Nonlongitudinal continuous variables (up to 36 weeks) such as 6-point SMPG, C-peptide, fasting insulin, fasting glucagon, HOMA2-IR, and HOMA2-%B will be analyzed using LOCF by fitting a linear model with pooled country, treatment, and baseline HbA1c strata as fixed effects, and the corresponding baseline value as a covariate. A data transformation may be applied if data are not normally distributed.

The 6-point SMPG consists of measurements before and 2 hours after each of 3 meals within the same day. Each of the time points of the 6-point SMPG, mean of the premeal values, mean of the postmeal values, mean of all 6 time points, breakfast excursion, mid-day excursion, dinner excursion, and mean of all 3 excursions for each scheduled postrandomization visit will be summarized separately.

6.10. Safety Analyses

The safety parameters to be analyzed include AEs, serious AEs (SAEs), AEs of special interest (AESIs), treatment-emergent AEs (TEAEs), safety laboratory analytes, vital signs, and electrocardiograms (ECGs). Adverse events of special interest are cardiovascular (CV) events, hypoglycemia and hyperglycemia, pancreatitis, thyroid C-cell hyperplasia and C-cell neoplasms, hypersensitivity reactions, injection site reactions, supraventricular arrhythmias and cardiac conduction disorders, acute gallbladder disease, and acute renal events.

All AEs will be coded using the Medical Dictionary for Regulatory Activities (MedDRA). Treatment-emergent AEs are defined as postbaseline events that are new events or preexisting conditions that worsened in severity after randomization using MedDRA term. The maximum severity level for baseline and postbaseline for each AE will be used as a criterion to determine TEAEs. If an AE occurs on the same date as the first dosing date with missing event occurring time, that event will be counted as a postbaseline event.

Unless otherwise specified, AEs will be reported using the MedDRA Preferred Term (PT) and/or System Organ Class (SOC). Selected AEs may be reported using MedDRA High Level Terms (HLTs) in addition to the SOC and PT, for consistency with other dulaglutide studies.

6.10.1. Adverse Events

Summary statistics will be provided for the following data: medical history and/or preexisting condition AEs, TEAEs, treatment-emergent AESIs, and study and/or treatment discontinuations due to AEs or death. The numbers and proportions of patients experiencing each corresponding AE will be reported by treatment.

For each patient, the primary AE analysis will be summarized up to the end of the treatment period or premature termination of the study, whichever comes first.

As supportive analyses, SAEs, TEAEs, and treatment-emergent AESIs for each patient will be summarized through the end of the study, including the Safety Follow-up Period.

The incidence of patients with at least 1 TEAE will be summarized by PT and by treatment group, and also by the SOC and PT.

A summary of TEAEs by maximum severity will be presented descriptively by treatment group.

6.10.1.1. Deaths, Other Serious Adverse Events, and Other Notable Adverse Events

All SAEs will be summarized by treatment by PT.

Patient listings for patient narratives will be generated.

6.10.1.2. Adverse Events of Special Interest

6.10.1.2.1. Cardiovascular Events

Summaries of adjudicated and investigator-reported CV events will be provided by treatment only if $\geq 1\%$ of patients have at least 1 event. The test statistics are detailed in Section 6.1.

The nonfatal CV AEs of interest are: myocardial infarction; hospitalization for unstable angina; hospitalization for heart failure; coronary interventions (such as coronary artery bypass graft or percutaneous coronary intervention); and cerebrovascular events, including cerebrovascular accident (stroke) and transient ischemic attack.

6.10.1.2.2. Hypoglycemia and Hyperglycemia

The rescue therapy definition in this section is based on the response in the CRF noting rescue therapy for severe, persistent hyperglycemia, which differs from “on-treatment with rescue,” as defined in Section 6.1.

6.10.1.2.2.1. Hypoglycemic Episodes

Detailed definitions for various categories of hypoglycemia are defined in the protocol (GBGL Protocol Section 9.2.2.2). For analyses purposes, the following main categories of hypoglycemia will be considered:

- **Documented symptomatic hypoglycemia** is defined as any time a patient feels that he/she is experiencing symptoms and/or signs associated with hypoglycemia, and has a documented plasma glucose (PG) level below the defined threshold.
- **Severe hypoglycemia** is defined as an episode requiring the assistance of another person to actively administer carbohydrate, glucagon, or other resuscitative actions. These episodes may be associated with sufficient neuroglycopenia to induce seizure or coma. Plasma glucose measurements may not be available during such an event, but neurological recovery attributable to the restoration of PG level to normal is considered sufficient evidence that the event was induced by a low PG concentration.
- **Total hypoglycemia** is defined as an episode with PG level below the defined threshold, regardless of symptoms, an episode of symptomatic hypoglycemia where PG level was not measured (ie, probable), and all severe hypoglycemia episodes.

Analyses of total and documented symptomatic hypoglycemia will include categories defined based on 2 PG cutoffs: PG ≤ 70 mg/dL (3.9 mmol/L) cutoff (Glucose Alert Level 1) and PG < 54 mg/dL (3.0 mmol/L) cutoff (Glucose Alert Level 2) (International Hypoglycaemia Study Group 2017). Per American Diabetes Association and European Association for the Study of

Diabetes recommendations, Glucose Alert Level 2 is considered clinically important hypoglycemia for reporting in results of clinical trials of glucose-lowering drugs. Analysis of hypoglycemia episodes with a PG ≤ 70 mg/dL (3.9 mmol/L) also will be included for comparability to prior studies in the dulaglutide development program.

In the analyses described above, hypoglycemia data will be censored at the time of receipt of rescue medication.

Additionally, a separate analysis will report all hypoglycemia events with PG < 54 mg/dL (3.0 mmol/L), regardless of symptoms, and all severe hypoglycemia episodes for the Safety Population including events that occurred after patients started new antihyperglycemic medications (including rescue medications). In recent regulatory interactions, FDA indicated that Level 2 hypoglycemia (PG < 54 mg/dL or PG < 3 mmol/L) represents a clinically meaningful degree of hypoglycemia and should be summarized as part of study results.

To avoid duplicate reporting, all consecutive PG values ≤ 70 mg/dL (3.9 mmol/L) occurring within a 1-hour period may be considered to be a single hypoglycemic event (Weinberg et al. 2010; Danne et al. 2013).

For each of the hypoglycemia categories, the incidence will be analyzed using the methods for analyses of categorical data described in Section 6.1, by randomized treatment. The rate of hypoglycemic episodes will be analyzed using a generalized linear mixed-effects model assuming negative binomial distribution for hypoglycemic episodes with pooled country and treatment as fixed effects and baseline HbA1c as covariate. The logarithm of days during active treatment period will be adjusted as an offset to account for possible unequal treatment duration between patients. This model will be implemented using SAS[®] procedure GLIMMIX using the log-link function. The predicted hypoglycemia rate per 1 year by treatment will also be presented. For rare hypoglycemic episodes such as severe hypoglycemia, Wilcoxon rank sum test will be used to compare the corresponding 1-year hypoglycemia rates between each investigational dulaglutide dose and dulaglutide 1.5 mg.

6.10.1.2.2.2. Severe, Persistent Hyperglycemia

Summaries (if appropriate) will be provided for patients initiating rescue therapy for events of severe, persistent hyperglycemia by each randomized treatment. The time to initiation of rescue therapy for severe, persistent hyperglycemia will be analyzed using PROC LIFETEST to generate Kaplan-Meier curves for each treatment. The summary reports including Kaplan-Meier curves will only be generated if $\geq 1\%$ of patients receive rescue intervention.

6.10.1.2.3. Pancreatitis

Summaries of adjudicated and investigator-reported pancreatic events will be provided by treatment. However, the summary will only be generated if $\geq 1\%$ of patients have pancreatic event(s). Determination of investigator-reported events will be through the “Acute pancreatitis” Standardized MedDRA Queries (SMQs) and a “Chronic pancreatitis” Lilly Search Categories (LSC) of the AE database.

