10.3.4. Safety Analyses

The safety endpoints will include incidence of AEs, adjudicated AEs, discontinuations due to AEs, SAEs, and TEAEs (defined as postbaseline events that are new events or preexisting conditions that worsened in severity after randomization), hypoglycemic and hyperglycemic episodes, and laboratory analytes. Unless otherwise specified, the ITT Population will be used for analyses of safety measures.

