10.3.4.2. Adverse Events

Adverse events will be coded from the actual term using the Medical Dictionary for Regulatory Activities (MedDRA) and reported with preferred terms and system organ class (SOC). Selected notable AEs of interest may be reported using high-level terms.

Summary statistics will be provided for overall AE, TEAEs, SAEs, study discontinuation due to AEs or death, and study drug discontinuation due to AEs. Counts and proportions of patients experiencing AEs will be reported for each treatment.

Summaries (if appropriate) of adverse events of special interest (AESI) defined in Section 9.2.2 will be generated.

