Table GBGL.1 shows the objectives and endpoints of the study.

Table GBGL.1. Objectives and Endpoints

Objectives	Endpoints

Primary To demonstrate that once weekly dulaglutide 4.5 mg and/or 3.0 mg is superior to dulaglutide 1.5 mg as measured by change from baseline in HbA1c at 36 weeks in patients with inadequately controlled T2D on concomitant metformin therapy.
	
 • The change in HbA1c from baseline

Secondary Efficacy: To demonstrate that once weekly dulaglutide 4.5 mg and/or 3.0 mg is superior to dulaglutide 1.5 mg for secondary efficacy parameters at 36 weeks (controlled for Type 1 error).
 
Safety: To compare each investigational dulaglutide arm (4.5 mg, 3.0 mg) to the 1.5 mg arm for selected safety parameters through 36 and 52 weeks (unless noted otherwise).
 
Pharmacokinetics (PK) and Pharmacodynamics (PD): To characterize dulaglutide PK and the dose and/or exposure-response relationships for key efficacy (eg, HbA1c and weight), and safety (eg, heart rate [HR]) endpoints.
	
 • The change in body weight from baseline • Proportion of patients achieving HbA1c target <7.0% (53 mmol/mol) • The change in fasting serum glucose (FSG) from baseline • Incidence of treatment-emergent adverse events (TEAEs) and discontinuation of study drug due to adverse events (AEs) • Adjudicated and confirmed cardiovascular and pancreatic AEs • Incidence of thyroid neoplasm AEs • Incidence of treatment-emergent (TE) dulaglutide anti-drug antibodies (ADA) and systemic hypersensitivity reactions • Changes from baseline in pulse rate • Electrocardiogram (ECG) parameters • Occurrence of hypoglycemic episodes • PK parameters (eg, maximum concentration [C_{max}], area under the curve [AUC]) at steady state • PD evaluations may include changes from baseline in HbA1c, body weight, and HR at Weeks 36 and 52

Objectives	Endpoints

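### The SAP tabulates adjudicated cardiovascular and pancreatic events by arm only if at least 1% of patients have one, so a named secondary safety endpoint may go unreported

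*SAP*

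**What the plan says.** Table GBGL.1, in section 4 of both the protocol and the SAP, lists "Adjudicated and confirmed cardiovascular and pancreatic AEs" as an endpoint under the secondary safety objective. That objective is a comparison of the 4.5 mg and 3.0 mg arms with the 1.5 mg arm through 36 and 52 weeks. Protocol 10.3.4 also names adjudicated events, with no frequency condition: "The safety endpoints will include incidence of AEs, adjudicated AEs, discontinuations due to AEs, SAEs, and TEAEs".

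The SAP sections that deliver the endpoint are conditional. For CV events, SAP 6.10.1.2.1 reads "Summaries of adjudicated and investigator-reported CV events will be provided by treatment only if" at least 1% of patients have an event. For pancreatic events, SAP 6.10.1.2.3 first promises a by-treatment summary and then adds "However, the summary will only be generated if $\geq 1\%$ of patients have pancreatic event(s").

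Four other passages bear on this:

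- SAP 6.10 classes both event types as events of special interest (AESIs): "Adverse events of special interest are cardiovascular (CV) events, hypoglycemia and hyperglycemia, pancreatitis".
- SAP 6.10.1 promises summaries, without a threshold, that include "TEAEs, treatment-emergent AESIs, and study and/or treatment discontinuations due to AEs or death".
- SAP 6.10.1.1 adds "All SAEs will be summarized by treatment by PT" and mentions listings for narratives.
- Protocol 10.3.4.2 is looser: "Summaries (if appropriate) of adverse events of special interest (AESI) defined in Section 9.2.2 will be generated".

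**The concern.** A secondary safety endpoint should have a planned output whatever the count turns out to be; for rare events, a low count is itself the result. Followed exactly, the SAP can leave this endpoint without one. Below the threshold, a reader would see investigator terms by arm but not which events the independent committee confirmed in each arm, and that confirmed count is the endpoint as named.

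The general tables do not fully stand in for it. They are built on preferred terms, and the SAP does not say that they carry adjudication outcomes. Protocol 9.2.2.3 sends severe or serious abdominal pain of unknown cause to the committee, so an event the committee confirms as pancreatitis could sit in those tables under a different term.

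The question matters in this programme. Protocol 3.2 reports that a monitoring committee stopped the 3.0 mg dose in an earlier study, partly because of pancreatic enzyme findings and heart-rate increases. The same section relies in part on adjudicated pancreatitis results to justify testing higher doses again.

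**Working it through.** **Denominator.** Protocol 10.1 and SAP 5.2 plan about 3000 screened with 40% screen failure: 3000 × (1 − 0.40) = 1800 randomized, and 1800 / 3 = 600 per arm. This agrees with the plan. Safety analyses use the Safety Population (SAP 6.2), taken here as about 1800.

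**What 1% means.** The text supports at least three readings:

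- Pooled: 0.01 × 1800 = 18 patients.
- Any one arm: 0.01 × 600 = 6 patients in at least one arm.
- Every arm: 6 patients in each of the three arms.

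Nor does it say whether confirmed events, investigator-reported events, or either count toward the 1%. If either counts, the trigger is easier to meet than the confirmed rate alone suggests.

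**Chance that the table is not produced.** The documents give no event rate. I therefore assume the same true rate p in every arm, where p refers to whatever event type counts. With binomial counts:

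- Pooled: P(X ≤ 17), X ~ Bin(1800, p).
- Any arm: q³, where q = P(Y ≤ 5), Y ~ Bin(600, p).
- Every arm: 1 − (1 − q)³.

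| Assumed rate p | Expected total (1800p) | q | No table, pooled | No table, any arm | No table, every arm |
|---|---|---|---|---|---|
| 0.5% | 9 | 0.9166 | 99.5% | 77% | 99.9% |
| 0.75% | 13.5 | 0.7033 | 86% | 35% | 97% |
| 1.0% | 18 | 0.4449 | 47% | 9% | 83% |
| 1.25% | 22.5 | 0.2397 | 14% | 1% | 56% |

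For example, at 1.0% on the any-arm reading, 0.4449³ = 0.088. For a 90% chance that the table is produced, the true rate must be about 1.31% (pooled) or 0.98% (any arm). The figures apply separately to the CV table and the pancreatic table.

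**What could go untabulated.** On the pooled reading, any total up to 17 produces no table. With none in the third arm, that includes confirmed splits between two arms of 12 vs 0 (two-sided Fisher p = 0.0005) and 14 vs 3 (p = 0.012). On the any-arm reading both would trigger the table, since 12 and 14 exceed 6. The most extreme two-arm split left out there is 5 vs 0 (p = 0.06).

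**Is there another route to the endpoint?**

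| SAP section | Condition | Shows the committee's result? |
|---|---|---|
| 6.10.1.2.1 CV | ≥1% | Yes |
| 6.10.1.2.3 Pancreatitis | ≥1% | Yes |
| 6.10.1 TEAEs, AESIs, discontinuations | None | Not stated |
| 6.10.1.1 SAEs by preferred term, narrative listings | None | Not stated |
| 6.10.1.4 Overdose (for contrast) | ≥1%, with a listing below it | Not applicable |

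Only the two conditional sections present adjudicated results. The overdose section pairs the same 1% rule with a fallback; these two do not.

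**The case against.** The best case for leaving the text alone has five parts.

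- **Discretion.** Protocol 10.3.4.2 allows AESI summaries where appropriate, and protocol 10.3.1 lets the SAP change methods without an amendment unless a principal feature changes. A 1% rule can be read as defining what is appropriate. It is a fair reading, but discretion over AESI tables does not remove an endpoint that Table GBGL.1 still names in both documents.
- **General versus specific.** The unconditional AESI promise in SAP 6.10.1 need not contradict the later sections, because a specific rule ordinarily qualifies a general one. This stands, and it softens any charge of outright contradiction. It also confirms that the specific rule governs and the table is withheld. If the general rule prevailed instead, AESI counts would be produced by arm, still without a stated adjudication result.
- **Little is lost.** Investigator terms remain visible by arm, so an imbalance in those terms would not be hidden. SAP 6.1 permits additional analyses. Events also accumulate between the two database locks, so a table missing at Week 36 might appear at Week 52. All true, and they limit the severity. None of them guarantees the confirmed count.
- **The probabilities say little about this trial.** They rest on assumed rates, and adjudication covers a broad set of CV events as well as suspected pancreatic cases. That is correct; the table shows a range and does not predict.
- **Thyroid and hypersensitivity carry the same rule.** SAP 6.10.1.2.4 and 6.10.1.2.5 have the same condition and also relate to endpoints in Table GBGL.1. They deserve reconciling, but there the individual investigator terms remain and only the grouping is lost. For CV and pancreatic events the adjudication result itself is lost.

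**Conclusion.** The concern holds. Applied as written, the SAP can leave the committee-confirmed CV and pancreatic counts by arm unreported, although they are a named secondary safety endpoint. It should be fixed. It is not critical, because the primary and alpha-controlled endpoints are untouched and investigator-reported events stay visible by arm.

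How likely the gap is depends on the event rate and on the unstated basis of the 1%. Across assumed common rates of 0.5% to 1.25%, with 600 per arm, the chance of no table runs from 99.5% down to 14% on the pooled reading and from 77% down to 1% on the any-arm reading. The every-arm reading makes omission likelier still. That a named endpoint's reporting turns on a choice not fixed in advance is part of the defect.

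**What to change.** Delete the 1% condition in SAP 6.10.1.2.1 and 6.10.1.2.3. State that n (%) by arm will always be tabulated for adjudicated-confirmed CV events and for adjudicated-confirmed pancreatic events, with investigator-reported events shown separately. Treat the tables as mainly descriptive, using the Fisher's exact test that SAP 6.1 already makes the default. If a threshold is wanted for detailed breakdowns or tests, keep it for those only and state its denominator and the event type that counts.

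As a minor point, reconcile the same condition in SAP 6.10.1.2.4 and 6.10.1.2.5 with the unconditional AESI summary in SAP 6.10.1.

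The cost is SAP wording and a few sparse tables with little power. No new data are needed: both event types already go to adjudication, and protocol 9.2.2.3 has the pancreatic result entered on an eCRF page. Sample size, power and alpha do not change.
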